## 8. SAFETY MONITORING

### 8.1 Overview

This section defines the types of AEs and outlines the procedures for appropriately collecting, grading, recording, and reporting them. Information in this section complies with 21CFR 312; ICH Guideline E2A: Clinical Safety Data Management: Definitions and Standards for Expedited Reporting; and ICH Guideline E-6: Guidelines for Good Clinical Practice; and applies the standards set forth in the CIT Common Terminology Criteria for Adverse Events.

The investigator is responsible for the detection and documentation of events meeting the criteria and definition of an AE or SAE as described in section 8.2 of this protocol. AEs and SAEs will be recorded in the source documents and on the appropriate electronic CRF(s). All data will be reviewed periodically by the independent study monitor, who may provide recommendations to NIAID about withdrawing any participant and/or terminating the study because of safety concerns.

### 8.2 Definitions

#### 8.2.1 Adverse Event

An adverse event (AE) is defined as any untoward or unfavorable medical occurrence associated with the subject's participation in the research, whether or not considered related to the subject's participation in the research (ICH E-6 Guidelines for GCP).

For this study, an adverse event will include any untoward or unfavorable medical occurrence associated with the following.

- **Study therapy:**
  - None
- **Study mandated procedures:**
  - Blood draws – Any AE occurring within 24 hours after a protocol mandated blood draw.
  - Metabolic testing – Any AE occurring within 24 hours after study-required metabolic testing.

Adverse events occurring outside the designated time parameters should also be reported if the investigator deems a possible association with a study mandated procedure.

Recording of adverse events in this trial will be limited to:

- cirrhosis
- renal insufficiency
- malignancy
- hypoglycemia
- all adverse events meeting the serious criteria outlined in section 8.2.4.

### **8.2.2 Suspected Adverse Reaction (SAR)**

A suspected adverse reaction (SAR) is any adverse event for which there is a reasonable possibility that the investigational study therapy or procedure caused the adverse event. For the purposes of safety reporting, 'reasonable possibility' means there is evidence to suggest a causal relationship between the study therapy or procedure and the adverse event. A suspected adverse reaction implies a lesser degree of certainty about causality than adverse reaction, which means any adverse event caused by a study therapy or procedure (21 CFR 312.32(a)).

### **8.2.3 Unexpected Adverse Event**

An adverse event or suspected adverse reaction is considered "unexpected" if it is not consistent with the risk information described in the protocol or other experience pertaining to study procedures in this population.

### **8.2.4 Serious Adverse Event**

An adverse event or suspected adverse reaction is considered "serious" if, in the view of either the investigator or DAIT/NIAID, it results in any of the following outcomes (21CFR312.32(a)):

- 1) Death.
- 2) A life-threatening event. An AE or SAR is considered "life-threatening" if, in the view of either the investigator or DAIT/NIAID, its occurrence places the subject at immediate risk of death. It does not include an AE or SAR that, had it occurred in a more severe form, might have caused death.
- 3) Inpatient hospitalization greater than 24 hours or prolongation of existing hospitalization.
- 4) Persistent or significant incapacity or substantial disruption of the ability to conduct normal life functions.
- 5) Congenital anomaly or birth defect.
- 6) An event that required intervention to prevent permanent impairment or damage.
- 7) An important medical event that may not result in death, be life threatening, or require hospitalization may be considered an SAE when, based on appropriate medical judgment, it may jeopardize the participant and may require medical or surgical intervention to prevent one of the outcomes listed above.

## **8.3 Grading and Attribution of Adverse Events**

### **8.3.1 Grading Criteria**

The study site will grade the severity of AEs experienced by CIT study subjects according to the criteria set forth in the *CIT-TCAE*. This document provides a common language to describe levels of severity, to analyze and interpret data, and to articulate the clinical significance of all AEs.

AE severity will be graded on a scale from 1 to 5 according to the following standards in the *CIT-TCAE* manual:

Grade 1 = Mild AE.

Grade 2 = Moderate AE.

Grade 3 = Severe and undesirable AE.

Grade 4 = Life-threatening or disabling AE.

Grade 5 = Death.

Table 4: General severity definition of adverse event

Grade 1	Mild	Transient or mild discomforts (< 48 hours), no or minimal medical intervention/therapy required, hospitalization not necessary (non-prescription or single-use prescription therapy may be employed to relieve symptoms, e.g. , aspirin for simple headache, acetaminophen for post-surgical pain).
Grade 2	Moderate	Mild to moderate limitation in activity some assistance may be needed; no or minimal intervention/therapy required, hospitalization possible.
Grade 3	Severe	Marked limitation in activity, some assistance usually required; medical intervention/therapy required hospitalization possible.
Grade 4	Life-threatening	Extreme limitation in activity, significant assistance required; significant medical/therapy intervention required hospitalization or hospice care probable.
Grade 5	Death	Death.

AEs, not included in the *CIT-TCAE* listing, should be recorded and their severity graded from 1 to 5 according to the General Grade Definition provided above.

All AEs will be reported and graded, by the PI or designee, whether they are or are not related to disease progression or study protocol.

### 8.3.2 **Definition of Attribution**

Attribution will only be determined and collected for serious adverse events.

The relatedness, or attribution, of an SAE to a study procedure will be determined by the site investigator. The site investigator will also record the determination of attribution on the appropriate eCRF and/or SAE report form. The relationship of an SAE (attribution of SAE) to a study procedure will be defined by using the descriptors provided below.

Table 5: Attribution of adverse events

Code	Descriptor	Definition
UNRELATED CATEGORY		
1	Unrelated	The adverse event is definitely not related to the study treatment.
RELATED CATEGORIES		
2	Possible	The adverse event might or might not be related to the study treatment. (This grade is assigned when uncertainty exists)
3	Definite	The adverse event is definitely related to the study treatment.

For additional information and a printable version of the CIT-TCAE manual, consult the CIT website: <http://isletstudy.org>.

## 8.4 Collecting and Recording of Adverse Events

### 8.4.1 Collection Period

AEs will be followed until resolution, stabilization, or until 30 days after a participant terminates from the study, whichever comes first.

### 8.4.2 Collecting Adverse Events

Adverse Events (including SAEs) may be discovered through any of these methods:

- Observing the subject.
- Receiving an unsolicited complaint from the subject.
- During their annual study visits and/or at the time of premature withdrawal from the study, subjects will be asked whether, in the past year:
  - They were hospitalized;
  - They had a medical issue requiring a visit to the emergency room or an urgent care clinic;
  - They experienced any severe hypoglycemic events;
  - They have been diagnosed with a malignancy; and
  - They have become pregnant or have plans for pregnancy.
- In addition, an abnormal value or result from a clinical or laboratory evaluation can also indicate an adverse event, as defined in Section 8.3, Grading and Attribution of Adverse Events.

### 8.4.3 Recording Adverse Events

The investigator will record adverse events and serious adverse events as described previously (Section 8.2, Definitions) on the appropriate case report form regardless of the relationship to study procedure.

Adverse events must be recorded by the site on the appropriate AE/SAE CRF within 5 business days of awareness.

Adverse events collected on a case report form.

Once recorded, an AE/SAE will be followed until it resolves with or without sequelae, or until the end of study participation, or until 30 days after the subject prematurely withdraws (without withdrawing consent)/or is withdrawn from the study, whichever occurs first.

#### **8.4.4 Reporting Serious Adverse Events**

##### **8.4.4.1 REPORTING OF SERIOUS ADVERSE EVENTS TO SPONSOR**

This section describes the responsibilities of the site investigator to report serious adverse events to the sponsor via the DCC eCRF. Timely reporting of adverse events is required by 21 CFR and ICH E6 guidelines.

Site investigators must report all serious adverse events (see Section 8.2.4, Serious Adverse Event), regardless of relationship or expectedness within 24 hours of discovering the event.

For serious adverse events, all requested information on the AE/SAE eCRF should be provided to the DCC. However, unavailable details of the event should not delay submission of the known information. As additional details become available, the AE/SAE eCRF should be updated and submitted.

##### **8.4.4.2 REPORTING OF ADVERSE EVENTS TO IRBS**

All investigators must report adverse events in a timely fashion to their respective IRBs in accordance with applicable regulations and guidelines.

##### **8.4.4.3 REPORTING PREGNANCY**

Any pregnancy that occurs during a clinical study that is using an investigational drug must be reported to the DCC utilizing the SAE report form. This report is for tracking purposes only. The investigator will counsel the subject and discuss the risks of continuing with the pregnancy and the possible effects on the fetus, and will encourage the subject to discuss those choices with her obstetrician. All pregnancies that are identified during the study must be followed to conclusion and the outcome of each must be reported using the follow-up SAE report form. A woman who wishes to become pregnant while on the study will be counseled as to her choices and, if she decides to stop using contraception, will be dropped from the study.

## **8.5 Review of Safety Information**

### **8.5.1 Medical Monitor Review**

The DAIT/NIAID and NIDDK Medical Monitors will receive monthly reports compiling new and accumulating information on AEs, SAEs, and pregnancies recorded by the sites on appropriate eCRFs.

In addition, the Medical Monitor will review and triage SAE and pregnancy reports received from the DCC.

### **8.5.2 DSMB Review**

The Data and Safety Monitoring Board (DSMB) will review safety data yearly during planned DSMB Data Review Meetings. Data for the planned safety reviews will include, at a minimum, a listing of all reported AEs and SAEs.

## 9. MECHANISTIC ASSAYS

### 9.1 Metabolic Testing

#### 9.1.1 Study Endpoints

Because the assessment of islet graft function is dependent on complex physiologic relationships between the graft and its recipient, no single test adequately addresses the viability of the transplant. The primary endpoint of duration of graft function addresses the clinically important outcome.

##### 9.1.1.1 GLYCEMIC CONTROL

Glycemic control will be assessed by HbA1c (%), which will be analyzed at the central laboratory.

##### 9.1.1.2 HYPOGLYCEMIA

An episode of severe hypoglycemia is defined as an event with one of the following symptoms: memory loss; confusion; uncontrollable behavior; irrational behavior; unusual difficulty in awakening; suspected seizure; seizure; loss of consciousness; or visual symptoms, in which the subject was unable to treat him/herself and which was associated with either a blood glucose level <54 mg/dL (3.0 mmol/L) or prompt recovery after oral carbohydrate, IV glucose, or glucagon administration.

##### 9.1.1.3 MIXED-MEAL TOLERANCE TEST (MMTT)

Basal (fasting) and stimulated glucose and C-peptide levels will be determined using the MMTT. Subjects will be instructed not to eat or inject short-acting (or bolus) insulin after 8 PM the night before the test. Evening or bedtime administration of long-acting insulin will be permitted, as will consumption of water. Subjects receiving CSII (insulin "pump" therapy) may remain on the basal rate of insulin. Subjects will arrive fasting to the transplant or diabetes clinic where the capillary BG will be checked. If the BG is <70 mg/dl (3.89 mmol/L) or >180 mg/dl (10 mmol/L), the test will be rescheduled for the next possible day. If the BG is 70 - 180 mg/dl (3.89 - 10 mmol/L), basal glucose and c-peptide levels will be drawn. Immediately after, the subject will receive 6 mL per kg body weight (to a maximum of 360 mL) of Boost® High Protein Drink (or a nutritionally equivalent substitute) to consume in 5 minutes starting at time = 0. Then, at time = 60 minutes and time = 90 minutes, stimulated glucose and C-peptide levels will again be drawn.

Each blood sample collected for c-peptide and glucose determination will be drawn according to University of Washington (Seattle, WA) SOP and will be shipped frozen to U of W for measurement in the core laboratory.

## 9.2 Immunologic Testing

Although insulin independence can be achieved via transplantation of an adequate number of viable, functional islets, a gradual reduction in the percent insulin independent patients occurs over time, with approximately 25% of patients still insulin free at 4 years post-transplant. Immune mediated islet destruction in the form of allorejection and/or recurrent autoimmunity, as well as attrition of a marginal islet mass due to exhaustion and/or toxicity of immunosuppressive agents, have all been postulated to play a role in islet loss. In order to begin to dissect the role of immune mediated reactions in allograft loss, tests will be done to determine if sensitization to donor allo- or islet autoantigens has occurred. In addition, maintenance of protective immunity in the setting of immunosuppression will be addressed.

While methods for determination of allo- and autoantibody have been extensively studied and are fairly well-established, reliable, reproducible and validated methods for assessment of T cell immunoreactivity to allo and/or autoantigens do not exist. For the most part, these techniques are time-consuming, technically demanding and require large blood volumes and significant staff time for set up and analysis of the resultant data. Several methods are undergoing testing in multiple T1D consortia (*e.g.*, ELISPOT, tetramer staining, T cell proliferation assays) to determine which tests provide the most reliable data with regards to distinguishing between patients with T1D vs. normal controls (for autoantigen) and to improve techniques for assessing recipient anti-donor reactivity.

### 9.2.1 Immune Assays

#### 9.2.1.1 ALLOANTIBODY

Development of alloantibody is generally associated with longer term graft loss. Development of alloantibody specific for 1 or 2 HLA antigens can now be defined using assays that incorporate HLA specific monoclonal antibodies. Alloantibody assessments will be performed at each site's laboratory for subjects who experience graft failure during participation in CIT08 and subsequently discontinue immunosuppression.

#### 9.2.1.2 ARCHIVED SERUM

In order to ensure that we will ultimately gain as much information as possible from these trials, and due to the ongoing development of assays such as T cell assays, serum will be archived for future analyses. Details for subjects regarding the archiving of samples and use for future assays are contained in the study's informed consent form. Subjects will have the option of whether or not they want to have samples archived and will indicate their choice on the informed consent form. A subject's choice regarding archiving samples will not affect his/her participation in the study.

Serum: Blood will be collected to obtain serum and archived in the NIDDK repository.

## 10. STATISTICAL CONSIDERATIONS AND ANALYTICAL PLAN

### 10.1 Study Endpoint Assessment

#### 10.1.1 Primary Endpoint

The primary endpoint is time to islet graft failure. The purpose of the analyses will be to estimate the probability of islet graft failure as a function of time from entry into the study. Life table methods will be used to estimate the survival curve and provide confidence intervals for the probability of islet graft survival for selected time points.

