### **3. SELECTION OF SUBJECTS**

#### **3.1 Inclusion Criteria**

Patients who meet all of the following criteria are eligible for participation in the study:

1. Participation in any of the following CIT parent studies: CIT02, CIT03, CIT04, CIT05, CIT06, and CIT07.
2. Willingness of participants to continue to use an approved method of contraception during and 4 months after study participation.
3. Ability to provide written informed consent.

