## 4. STUDY DESIGN

This is an open-label, multi-center cohort study for participants from the CIT02, CIT03, CIT04, CIT05, CIT06, and CIT07 studies who continue to have islet graft function. These participants will continue immunosuppressive medications under CIT08 and will be assessed for islet function on an annual basis.

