### 4.1 Study Endpoints

#### 4.1.1 Primary Endpoint

The primary endpoint is duration of sustained **islet allograft function** as determined by evidence from MMTT of c-peptide production at each anniversary of the final transplant. A c-peptide level greater than or equal to 0.3 ng/mL at 0, 60, or 90 minutes will be considered evidence of islet allograft function.

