### 7.2 Follow-up Visits

Subjects will be followed in this study after termination from the CIT parent study until the end date of the CIT08 study. Follow-up is comprised of quarterly visits done locally for safety monitoring and annual visits at the study center to assess graft function (if applicable) and safety.

Retrospective medical chart review will be conducted as needed to collect available follow-up information due to:

- delayed enrollment in CIT08 after termination from the CIT parent study
- the time period between termination from CIT08 prior to extension of the duration of follow-up and subsequent re-enrollment

This retrospective chart review will collect evidence of graft failure in addition to the follow-up assessments outlined in Appendix 1.

Subjects are allowed to concurrently enroll in and be screened for a non-CIT islet transplant study at any point during participation. Once study treatment in the non-CIT study is initiated, they will be withdrawn from CIT08 (see section 6.1).

Subjects with confirmed **graft failure** will not complete metabolic assessments. Subjects who experience graft failure and subsequently stop immunosuppression will have alloantibody assessed 3 months after their last dose of immunosuppression.

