### 7.3 Visit Windows

If the screening visit occurs within 90 days of the subject's final parent study visit, the results from the final parent study visit should be used. If the screening visit occurs more than 90 days after the final parent study visit, then the screening assessments must be repeated. Annual study visits will occur within plus or minus 30 days of the anniversary of the subjects' last parent study visit. Quarterly local visits will occur within plus or minus 14 days.

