#### 10.1.2 Secondary Endpoints

Insulin usage will be estimated from the one-week self report values. Estimates of population means and confidence intervals for those means will be reported for each follow-up visit. Linear mixed models methods will be used to describe the profile of change with time.

Numbers of severe hypoglycemic events will be estimated from the self report values obtained at each follow-up visit. Estimates of population means and confidence intervals for those means will be reported for each follow-up visit. Linear mixed models methods with appropriate likelihood functions will be used to describe trends with time.

HbA1c and serum creatinine levels will be measured at central laboratories at study entry and at the annual follow-up visit. GFR will be estimated using the updated CKD-EPI method. Estimates of population means and confidence intervals for those means will be reported for each follow-up visit. Linear mixed models methods will be used to describe trends with time.

Incidence of serious adverse experiences will be tabulated by body system and MedRA code. Life table methods will be used to estimate mortality rates.

The overall incidence of alloantibody conversion will be reported as a rate per 100 days of follow-up. A 95% confidence interval for the rate will be computed using boot-strap methods.

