## Appendix 1. Schedule of Events for Extended Follow-up

Visit schedule based on anniversary of last islet transplant in CIT parent study; visit schedule repeats each year.	Timing	SC	Local Visits 			On-Site Visit
			3 month	6 month	9 month	Anniversary of Final Islet Transplant
	Visit #	0	See MOP for Table of Visit Numbers			
Visit Window (specified in days)		- 90	±14	±14	±14	± 30
GENERAL ASSESSMENTS						
Informed Consent		X				
Evaluate Inclusion/Exclusion Criteria		X				
Physical Exam		X 				X
AE /Hypoglycemic Events/Toxicity Assessment 		X 	X	X	X	X
Calculated GFR		X 				X
Insulin use		X 	X	X	X	X 
Urine pregnancy test (females)		X				
LOCAL LABORATORY ASSESSMENTS						
CBC (WBC + Diff & Plat) 		X 	X	X	X	X
Chemistry 		X 	X	X	X	X
Lipids 		X 				X
Alloantibody		Collect 3 months after immunosuppressive medication is stopped following graft failure.				
CENTRAL LABORATORY/METABOLIC ASSESSMENTS						
HbA1c 		X 				X
Fasting serum gluc/c-pep & serum creatinine 		X 				X
MMTT 		X 				X
CARDIOVASCULAR ASSESSMENTS						
Carotid intimal thickness (IMT)		Collect at 5 years post-initial-islet transplant visit in subjects who completed the baseline carotid IMT assessment in their CIT parent study. 				
IMMUNOSUPPRESSION LEVELS						
Blood Trough Levels (if applicable) 		X 	X	X	X	X
Visit schedule based on anniversary of last islet transplant in CIT parent study; visit schedule repeats each year.	Timing	SC	Local Visits 			On-Site Visit
			3 month	6 month	9 month	Anniversary of Final Islet Transplant
	Visit #	0	See MOP for Table of Visit Numbers			
Visit Window (specified in days)		- 90	±14	±14	±14	± 30
MECHANISTIC ASSAYS - University of Pennsylvania Sub-Study Only						
Autoantibody 				X		X
Immunophenotyping 				X		X
Cytokine profiling 				X		X
Glucose-potentiated arginine 						X
ARCHIVED SAMPLES						
Serum						X

---

 These visits are performed locally but can be done on site if preferred.

 Only collect if screening is  $\geq 90$  days since final parent study visit. Otherwise, results from final parent study visit should be used for screening (Visit 0).

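### CIT08's primary analysis counts time from study entry although its endpoint is tied to the final transplant, and its sections disagree on whether failed grafts enter

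*Protocol*

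**What the plan says.** The file holds two protocols. This point concerns the second, the CIT08 extended follow-up study; section numbers are CIT08's unless CIT04 is named.

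- **Endpoint.** The synopsis and Section 4.1.1 define the primary endpoint as the length of time the graft works, judged by "c-peptide production at each anniversary of the final transplant".
- **Analysis.** Section 10.1.1 restates this as time to graft failure and uses life tables to "estimate the probability of islet graft failure as a function of time from entry into the study".
- **Entry.** The synopsis starts CIT08 follow-up once the subject has left the parent study. CIT04's synopsis ends that study 24 months after the final transplant. Section 7.2 allows for late enrolment, and for subjects who left CIT08 and re-enrolled.
- **Who enters.** Section 4 describes participants "who continue to have islet graft function". Section 3.1 asks for "Participation in any of the following CIT parent studies", plus contraception and consent. Neither it nor Section 3.2 mentions graft function.
- **Visit anchor.** Section 7.3 says "Annual study visits will occur within plus or minus 30 days of the anniversary of the" last parent-study visit. Appendix 1 says "Visit schedule based on anniversary of last islet transplant in CIT parent study".
- **Alloantibody.** Section 4.1.2 asks whether alloantibody is present in subjects whose graft has failed and who are off immunosuppression. Under Section 7.2 such subjects "will have alloantibody assessed 3 months after their last dose of immunosuppression", and Appendix 1 schedules no other test. Section 10.1.2 says: "The overall incidence of alloantibody conversion will be reported as a rate per 100 days of follow-up".
- **HbA1c.** Section 10.1.2 reports means at every follow-up visit. Appendix 1, footnote 7, stops collection once failure is confirmed.

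**The concern.** The analysis as written does not estimate the endpoint as written. The endpoint is organised around transplant anniversaries, while the analysis clock starts at an administrative date that falls at a different graft age for each subject. Subjects who re-enrolled have two possible entry dates, and Section 10.1.1 does not say which one counts.

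The risk set is also unsettled. Under Section 4, grafts that failed before entry never appear. Under Section 3.1 they may appear already failed, and a life table needs a rule for them at time zero.

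At stake is whether the main durability result can be set beside graft survival reported from transplant. Two secondary analyses have a related fault: an antibody rate whose follow-up days are not time at observed risk, and HbA1c means that silently describe only subjects without confirmed graft failure.

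**Working it through.** CIT08 states no expected graft survival, event count or power, so there is no figure to reproduce. All sizes below are illustrations.

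**Inputs.** S(t) is the share of transplanted grafts working t years after the final transplant; e is the time from that transplant to CIT08 entry.
- S(5) = 0.80, from CIT04 Section 1.5.5.1, which gives it as an upper figure for C-peptide production at 5 years.
- e = 2 years, from CIT04's 24 months; e = 1 and 3 are assumed as a range.
- The hazard shape is assumed (Weibull, shape 0.5 to 1.5).

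**Step 1: what the entry clock estimates.** With functioning grafts only, survival t years after entry is S(e+t)/S(e).

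**Step 2: same graft age.** A subject entering at year 2 reaches graft age 5 at t = 3, where the curve reads S(5)/S(2).
- Constant hazard: −ln(0.80)/5 = 0.0446 per year; exp(−3 × 0.0446) = 0.875, against 0.80.
- If S(5) were 0.50: ln 2/5 = 0.1386 per year; exp(−3 × 0.1386) = 0.66, against 0.50.

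Because S(2) cannot exceed 1, this reading can never fall below S(5), whatever the hazard.

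**Step 3: the curve's own axis.** Compare 5 years after entry, S(7)/S(2), with 5 years after transplant, S(5) = 0.80.

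| Weibull shape | Same graft age, S(5)/S(2) | 5 years on entry clock, S(7)/S(2) |
|---|---|---|
| 0.5 (falling hazard) | 0.921 | 0.884 |
| 0.75 | 0.895 | 0.839 |
| 1.0 (constant) | 0.875 | 0.800 |
| 1.25 | 0.859 | 0.764 |
| 1.5 (rising hazard) | 0.846 | 0.731 |

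The middle column is always above 0.80. The last column lies on either side of it. With an early loss of 5, 10 or 15% followed by a constant hazard, the 5-year entry-clock value is 0.80/0.95 = 0.842, 0.80/0.90 = 0.889 or 0.80/0.85 = 0.941.

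The documents give no hazard shape for C-peptide failure. The only time course is for insulin independence (CIT04 Section 1.4.1.1): 72% at year 1 falling to 28% at year 3, and 79% falling to 20%. The implied yearly hazards are −ln(0.72) = 0.33 then ln(0.72/0.28)/2 = 0.47, and −ln(0.79) = 0.24 then ln(0.79/0.20)/2 = 0.69. These rise, but for a different outcome.

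**Step 4: mixed graft ages.** The 5-year entry-clock value for e = 1, 2 and 3 is 0.865, 0.884 and 0.896 at shape 0.5; 0.800 throughout at shape 1; and 0.761, 0.731 and 0.706 at shape 1.5. Unless the hazard is constant, the pooled curve depends on when subjects happened to enrol.

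**Step 5: visit anchor.** CIT04 Appendix 4 places the week-52 visit of the additional year 52 weeks after day 365: 365 + 52 × 7 = day 729, against a second anniversary at day 730. The anchors nearly coincide for completers, well inside the 30-day window. Early terminators have no such alignment.

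**Step 6: alloantibody.** Suppose 5 of 10 tested subjects are positive (assumed).
- Denominator of all 75 subjects for an assumed 3 years: 75 × 3 × 365 = 82,125 days; 5/82,125 × 100 = 0.006 per 100 days.
- Denominator of the ten tested, about 90 days each: 900 days; 5/900 × 100 = 0.56 per 100 days.

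The same data give rates about 91 times apart (82,125/900), and Section 10.1.2 does not choose between them. The proportion is 50%, with exact 95% interval 18.7% to 81.3%, as in CIT04's Table 5 for 5 of 10.

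**The case against.** The best defence is that survival from entry is a coherent quantity, openly labelled, and fits a study whose purpose (Sections 1.3 and 1.4.3) is follow-up beyond the parent study. Section 4.1.1 fixes when function is assessed; it does not say in words that duration is counted from transplant. Chart review under Section 7.2 collects evidence of graft failure during enrolment gaps. Delayed-entry rules are ordinary SAP content. CIT08 has no hypothesis, decision threshold or stopping rule.

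Much of this stands, and it rules out two stronger readings. A reader might infer that the curve has no interpretable time axis; it has one, conditional on reaching CIT08. A reader might also infer that the plan overstates durability. The documents do not support that as a general claim: under a constant hazard there is no bias on the curve's own axis, and under a rising hazard it lies below survival from transplant. It is necessarily too high only against all transplanted grafts at the same graft age, and only if Section 4 governs.

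Three things survive. Section 10.1.1 itself fixes the time origin, so the choice was not left to the SAP, and Section 10.3 requires an amendment to change a principal feature. Chart review captures failures in the gap, but nothing says where a failure before entry goes on an entry clock. And Sections 3.1 and 4 cannot both define the risk set.

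On the secondary points, labelling HbA1c means is a reporting matter. The alloantibody endpoint is minor and absent from the CIT08 synopsis, but one scheduled test per selected subject still does not support a rate over follow-up time.

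**Conclusion.** The point holds as a mismatch between the stated endpoint and the stated analysis, together with a conflict over who enters. If Section 4 governs, the curve is conditional on function at entry and cannot be read as survival since transplant. At graft age 5, for entry at year 2, the illustration gives 87.5% against 80% under a constant hazard, and 84.6% to 92.1% over the Weibull shapes tried. If Section 3.1 governs, the handling of already-failed grafts at time zero is undefined, and the curve is not simply conditional on function at entry.

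These sizes rest on an upper-end 80% figure from earlier experience, assumed hazard shapes and an assumed entry delay. The other parent studies' follow-up lengths are not shown. The visit-anchor conflict is small for CIT04 completers and larger for early terminators. As CIT08 is single-arm and descriptive, this should be fixed, but it does not invalidate the study.

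**What to change.** - **Section 10.1.1.** Set time zero at the final parent-study transplant, with delayed entry at CIT08 enrolment and only functioning grafts in the risk set. State which enrolment counts for re-enrolled subjects and how failures found by chart review are placed. Delayed entry removes the mixing of graft ages but cannot recover failures before the earliest entry; including parent-study data does, and is preferable. Failing both, label the curve as conditional on function at CIT08 entry.
- **Sections 3.1 and 4.** Reconcile them on whether subjects with failed grafts enrol. If they do, keep them for safety follow-up and say how they are handled in the primary analysis.
- **Section 7.3.** Reconcile the visit anchor with Section 4.1.1 and Appendix 1.
- **Section 10.1.2.** Report alloantibody as the proportion positive among those tested, with an exact interval. Label HbA1c means as among subjects without confirmed graft failure.

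The cost is mainly protocol and SAP wording. Appendix 1 already schedules visits by transplant date, and Sections 7.1 and 7.3 already reuse parent-study results. Linking full parent-study data may cost more, because the documents do not say that one centre holds the data of all six studies.
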